### Protocol Synopsis

Title	Randomized feasibility study of discontinuation versus continuation of immunosuppressive therapy (IST) in patients with chronic Graft Versus Host Disease (GVHD)
Short Title	Functional Tolerance after Allo HCT
Study Design	Randomized prospective study
Study Objectives	
Primary Objective. Assess feasibility of enrolling and randomizing patients with chronic GVHD to discontinuation versus continuation of IST.
 
Secondary Objectives.
 
 
- Assess feasibility of enrolling and randomizing patients who are not local, and evaluate the quality of data received for those patients.
 
- Assess whether prolonged IST decreases the need for pulses of high dose IST.
 
- Evaluate the effect of prolonged IST on chronic GVHD manifestations and severity, risk of relapse, infection and organ toxicity.
 

Study Endpoints	
Primary Endpoints.
 
 
- Number of patients enrolled on the study (signed consent) in 2 years
 
 
Secondary Endpoint.
 
 
- Successful randomization of patients
 
- Compliance with treatment and data collection as outlined in the protocol
 
- Rate of IST resumption (discontinuation arm)/increase IST dose (continuation arm) by 12 months after randomization
 
- New chronic GVHD manifestations and/or worsening of existing manifestations, recurrent malignancy by 12 months after randomization, grade <math>\geq 3</math> infections, and grade <math>\geq 3</math> organ toxicity.
 

Accrual Objective	40 (20 patients on each arm)
Study Duration	2 year accrual period; 12 month active follow-up after randomization; Long term annual follow up via chart review.
Stopping Rules	Accrual of less than 12 patients in the first year
Treatment Description	IST continuation for 9 months on the continuation arm. Taper IST to off as planned in the discontinuation IST arm.
Inclusion Criteria	
 
1. Prior allogeneic stem cell transplant, with any graft source, donor type, and GVHD prophylaxis.
 

	

2. On only one systemic immunosuppressive agent for chronic GVHD with a plan to stop all systemic IST. Hydrocortisone or prednisone continued for treatment of adrenal insufficiency is not considered a systemic IST.

3. No evidence of malignancy at the time of enrollment.

4. Agreement for evaluation at the transplant center at the time of study enrollment, and then every 3 months at the transplant center or by local provider for 12 months after randomization

5. Agreement to be contacted by phone or e-mail for health status evaluation for up to 3 years

6. Signed, informed consent

Exclusion Criteria	

1. Inability to comply with study procedures

2. Pregnancy

## 1. Background and Rationale

Patients who received allogeneic hematopoietic cell transplantation (HCT) typically require administration of immunosuppressive treatment (IST) for at least 6 months in order to prevent or treat graft-versus-host disease (GVHD). GVHD is the most serious and common complication of allogeneic HCT. Significant acute GVHD occurs in 20-50% of patients,(1-3) and chronic GVHD occurs in 30-60% of patients who survive more than 100 days after transplantation.(3, 4) Duration of IST is typically prolonged once patients develop GVHD. Particularly, duration of IST in patients who have chronic GVHD is reported to exceed 2-3 years.(5, 6) While IST is important to reduce mortality and morbidity associated with GVHD, it may increase risks of infection, recurrent malignancy and secondary malignancy.(7)

“Immunologic tolerance” may be defined as the absence of immune-mediated injury when immunosuppressive medications are no longer given. Unlike solid organ transplantation,(8) many patients after allogeneic HCT can achieve sufficient “functional” tolerance even after development of GVHD, and can eventually stop all IST permanently without developing active manifestations of GVHD. However, many patients, especially those with chronic GVHD, develop GVHD exacerbation and require resumption of IST. Currently, there are no clinical or biological predictors for successful IST discontinuation, and management of chronic GVHD patients consists of repeated attempts to taper and stop IST.

A recent retrospective evaluation of 250 adult patients who received systemic treatment for chronic GVHD at the Fred Hutchinson Cancer Research Center (FHCRC)/Seattle Cancer Care Alliance (SCCA) demonstrated that although 51% patients were able to stop IST at least one time, 46% of these patients required resumption of IST after a median of 3.4 months off therapy (IQR 2.1-8.0), due to GVHD exacerbation (9). Among patients stopping IST a second time, 30% restarted at a median of 6 months.

Resumption of IST for chronic GVHD exacerbation may increase the morbidity and mortality of patients, since common practice is to reinstitute high doses of IST initially, followed by a taper again to the lowest dose. Additionally, GVHD may fail to be controlled after resumption of IST, or irreversible organ damage may occur each time GVHD symptoms flare.

A potential alternative approach to the current practice of repeated attempts to taper and stop IST is continuation of IST.

The purpose of this study is to enroll a cohort of patients with chronic GVHD whose treating physician is planning to taper their IST to off, and to randomize them to either discontinuation of IST (standard approach) or continuation of IST for another 9 months (investigational approach), in order to evaluate the effect of prolonged IST on chronic GVHD control, with the hypothesis that this approach would decrease the risk of GVHD exacerbation and decrease the need to resume high doses of IST. The rational for the 9 months extended IST in the continuation IST arm is retrospective data demonstrating

that >75% of patients who resumed IST after discontinuation, restarted within 9 months of IST discontinuation.

The rationale for the feasibility study is that a large sample size is needed to demonstrate statistically significant differences between the two treatment approaches. Thus, prior to proceeding with a large study we need to conduct a feasibility study to evaluate whether patients can be enrolled, randomized, and follow their assigned treatment, and to assess whether the observations about IST resumption in the retrospective study appear accurate. We acknowledge the heterogeneity among the target patient population (e.g. donor and stem cell source, time since transplant, and IST), but despite this heterogeneity when patients are ready to taper IST they are more similar than different in their clinical status. Information from this feasibility study are necessary to help us design a larger study and apply for external funding. In the larger study, we plan to use stratified randomization to help balance underlying patient and transplant characteristics.

Biological samples will be collected during the study to analysis of blood profiles and cellular signatures of “functional” tolerance and biomarkers of GVHD exacerbation.

## **2. Objectives**

### 2.1 Primary Objective

Assess feasibility of enrolling and randomizing patients with chronic GVHD to discontinuation (standard of care) versus continuation (investigation) of IST.

### 2.2 Secondary Objectives

- Assess feasibility of enrolling and randomizing patients who are not local, and evaluate the quality of data received for those patients.
- Assess whether prolonged IST decreases the need for pulses of high dose IST.
- Evaluate the effect of prolonged IST on chronic GVHD manifestations and severity, risk of relapse, infection and organ toxicity.

## **3. Endpoints**

### 3.1 Primary Endpoint

- Number of patients enrolled on the study (signed consent) in 2 years

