### 3.2 Secondary Endpoint

- Successful randomization of patients
- Compliance with treatment and data collection as outlined in the protocol
- Evaluate enrollment rate and quality of data of patients who are not local
- Rate of IST resumption (discontinuation IST arm)/increase IST dose (continuation IST arm) by 12 months after randomization

- New chronic GVHD manifestations and/or worsening of existing manifestations, recurrent malignancy by 12 months after randomization, grade  $\geq 3$  infections, and grade  $\geq 3$  organ toxicity.

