#### **6. Study Procedures**

##### **6.1 Study Design**

We plan to enroll 40 patients in 2 years. Patients are eligible for enrollment at any time after an allogeneic transplant, as long as they were diagnosed with chronic GVHD, are on one immunosuppression agent, and are planning to withdraw all IST. Patients will be randomized to either IST discontinuation (following standard of care practice) or continuation of IST for an additional 9 months (investigational). If patients are enrolled on the study prior to reaching the IST dose that the attending physician recommends

they continue should they be randomized to the continuation IST arm, randomization will take place before the patient gets to the IST dose that would be continued if they are randomized to the IST continuation arm (investigational arm). If patients are enrolled on the study while they are already taking the IST dose that the attending physician recommends they continue should they be randomized to the continuation IST arm, randomization will take place at time of enrollment (Figure 1). Randomization will occur within three months of study enrollment. Patients will be actively followed for 12 months after randomization. After active participation will continue long term annual follow up via chart review.

Patients on the discontinuation IST arm will have their IST tapered and discontinued per the plan of the treating physician, while patients on the continuation IST arm will continue a fixed dose IST for an additional 9 months with no taper. After 9 months, IST may be tapered.

The dose of IST to be continued, if a patient is randomized to the continuation IST arm, will be determined by the attending physician at the time of enrollment based on the following overarching guidelines in the table below:

Immunosuppressive therapy	Age 18 years	Age <18 years
Cyclosporine	Continuation dose should result in a level < 120 ng/mL	
Tacrolimus	Continuation dose should result in a level < 5 ng/mL	
Sirolimus	Continuation dose should result in a level < 3 ng/mL	
Mycophenolate mofetil	Continuation dose ≤ 500 mg BID	Continuation dose ≤ 7.5 mg/kg BID
Prednisone	< 20 mg/day or < 40 mg every other day	< 0.25 mg/kg/day or < 0.5 mg every other day
Any other agent	Defined by the treating physician at the time of enrollment	

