# 7. Statistical Considerations

## 7.1. Statistical Analysis Plan

### 7.1.1. Primary Endpoint

The primary objective of this study is to assess feasibility of enrolling and randomizing patients with chronic GVHD to discontinuation (discontinuation IST arm; standard of care) versus prolonged continuation of IST (continuation IST arm; investigational arm).

Feasibility will be assessed by accrual rate of 20 patients per year. Early stopping of the accrual to the study is low accrual rate defined as less than 12 patients enrolled in the first year.

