### 7.1.2. Secondary Endpoints

The secondary objective of this study includes three parts: 1) treatment compliance including rate of patient reaching randomization and rate of patients following study specific IST management based on study arm; 2) assess feasibility (enrollment and data collection) for patients who are not local; and 3) assess whether continuation IST decreases the need for pulses of high does IST and efficacy and safety evaluation of continuation IST arm

Secondary endpoint analyses will be descriptive. The analyses will be conducted by overall population, patients who are not local, and by arm, as applicable.

The summary statistics for continuous variables will include sample size, mean, standard deviation (SD), median, minimum and maximum for both baseline and post-baseline measurements (if applicable). The summary statistics for categorical variables will include sample size, frequency and percentages. The difference between two arms will be examined if applicable. Fisher's exact test will be proposed to test the difference between two arms for categorical variables.

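### The primary objective covers enrolling and randomizing, but the only primary endpoint and feasibility criterion count consents, so the criterion can be met however few patients are randomized

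*Combined protocol and SAP*

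**What the plan says.** Section 2.1 states the primary objective: "Assess feasibility of enrolling and randomizing patients with chronic GVHD to discontinuation (standard of care) versus continuation (investigation) of IST". Section 7.1.1 and the Synopsis repeat both parts.

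The Synopsis and Section 3.1 list one primary endpoint: "Number of patients enrolled on the study (signed consent) in 2 years". Section 7.1.1 gives one criterion: "Feasibility will be assessed by accrual rate of 20 patients per year". The only stopping rule is fewer than 12 patients in the first year. Section 4 words it as accrual, and Section 7.1.1 as patients enrolled.

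Randomization is a secondary endpoint in Section 3.2 ("Successful randomization of patients"). Section 7.1.2 places it under "treatment compliance including rate of patient reaching randomization" and says that secondary endpoints are analysed descriptively. No target is attached.

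On timing, Section 6.1 says "Randomization will occur within three months of study enrollment". Under Sections 6.1 and 6.5, patients already at the dose that might be continued are randomized at enrollment. Section 6.2 also allows enrollment before that dose is reached. Section 6.5 says that patients not randomized within three months leave active data collection and are followed by chart review.

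**The concern.** Consent and randomization are separate events for some patients by design, and the primary criterion sees only the first. A patient who signs consent and is never randomized counts towards 20 per year exactly as a randomized patient does.

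Section 1 says that the study is needed, before a large randomized trial, to "evaluate whether patients can be enrolled, randomized, and follow their assigned treatment". How many consenting patients go on to be randomized is a central part of what the larger trial needs to know. As written, the enrolling half of the primary objective has a criterion that it could fail and the randomizing half has none. If the rate proves low, whether it is acceptable will be judged after the data are seen.

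**Working it through.** **1. Objective against criterion**

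| Item | Enrolling | Randomizing |
|---|---|---|
| Primary objective (2.1, 7.1.1) | yes | yes |
| Primary endpoint (3.1) | signed consents in 2 years | none |
| Feasibility criterion (7.1.1) | 20 per year | none |
| Stopping rule (4, 7.1.1) | fewer than 12 in year 1 | none |
| Secondary, descriptive (3.2, 7.1.2) | non-local enrollment | rate reaching randomization, no minimum |

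With 40 consents in two years, 40/2 = 20 per year, so the criterion is met whether 40, 20 or 0 patients are randomized.

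**2. The plan's own figure.** Section 7.2 states 83% power with 20 per arm, 75% against 30%, two-sided level 0.10. The test named in Section 7.1.2 is Fisher's exact test. Its power is the sum, over all x and y from 0 to n, of Bin(x; n, 0.75) × Bin(y; n, 0.30), keeping the outcomes with Fisher p ≤ 0.10. For n = 20 this gives 82.3%, so the stated figure reproduces. It needs 40 *randomized* patients.

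**3. How far consents and randomizations could part.** The documents give no attrition figure, so both inputs here are assumptions. Let f be the share of consents already at the continuation dose (all taken as randomized) and r the share of the others randomized within three months. The proportion randomized is f + (1 − f) × r. For example, f = 0.25 and r = 0.4 give 0.25 + 0.75 × 0.4 = 0.55, or 22 of 40.

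| f | r = 0.4 | r = 0.6 | r = 0.8 |
|---|---|---|---|
| 0.25 | 22 | 28 | 34 |
| 0.50 | 28 | 32 | 36 |
| 0.75 | 34 | 36 | 38 |

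The range is 22 to 38 randomized, or 11 to 19 per year, and every cell meets the criterion equally. Clopper-Pearson 95% intervals for the proportion are 38–71% for 22/40, 53–83% for 28/40, 64–91% for 32/40 and 83–99% for 38/40.

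**4. Effect on the Section 7.2 comparison.** The formula of step 2 with equal arms gives:

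| Randomized of 40 consents | Per arm | Fisher power |
|---|---|---|
| 40 | 20 | 82% |
| 32 | 16 | 76% |
| 28 | 14 | 65% |
| 20 | 10 | 52% |

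The exact test is discrete, so power does not fall smoothly between these points. Conversely, randomizing 40 would take 40/0.9 ≈ 45, 40/0.8 = 50 or 40/0.7 ≈ 58 consents (rounded up) at 90%, 80% or 70% randomized.

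**5. How a minimum would behave.** For illustration only, take a minimum observed proportion of 75%. The probability of meeting it is P(X ≥ 0.75n) with X binomial(n, p). The case n = 24 is 12 consents per year for two years, the lowest rate that passes the first-year rule.

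| True proportion p | n = 40 (30 or more) | n = 24 (18 or more) |
|---|---|---|
| 0.90 | 99.9% | 99% |
| 0.80 | 84% | 81% |
| 0.70 | 31% | 39% |
| 0.60 | 3.5% | 10% |

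**The case against.** The strongest reply is that randomization is already covered. It is the first secondary endpoint, its rate is a planned analysis, and the three-month window and the handling of unrandomized patients are set in advance. Section 7.1.1 says that feasibility is assessed by accrual, not that it must be declared at 40 consents, and a sensible reader would not call a study with very few randomized patients feasible. This stands in part: nothing is hidden. But good sense on the reader's part is not a criterion, and the plan offers no other.

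A second reply is that accrual may already mean randomized patients, because the Synopsis gives the objective of 40 as 20 per arm and Section 7.2 also speaks of 20 in each arm. Against this, Section 3.1 defines enrollment as signed consent, Section 6.1 says "We plan to enroll 40 patients in 2 years", and Section 7.1.1 counts patients enrolled. If randomized patients were meant, the text needs correcting anyway.

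Third, the attrition range has no documentary basis, and the gap may be small: some patients are randomized at enrollment, the others do not first have to reach the continuation dose, and all have consented to a randomized study. This is fair. The range shows what the criterion would tolerate; it does not forecast attrition.

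Finally, a threshold is partly a matter of preference in a study sized by availability, and a 75% cut-off would misclassify at times (step 5 shows 16% failing at a true 80% and 31% passing at a true 70%). That bears on which minimum to choose and supports reporting an interval with it. It does not justify leaving half of the primary objective without a criterion.

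**Conclusion.** The concern holds. The mismatch is established by the text and does not depend on any assumed rate: the primary objective has two parts, the primary endpoint and feasibility criterion measure one, and a consented patient can go unrandomized and still count. Its practical size is unknown because the documents give no attrition figure. Under the assumed ranges (25% to 75% already at the continuation dose, 40% to 80% of the rest randomized in time), the same reported 20 per year could stand for 11 to 19 randomized per year. The 83% power statement is correct but presupposes that all 40 patients are randomized. It is not the basis of the sample size, so its loss is a secondary consequence. The point should be fixed; it weakens the primary conclusion but hides no data.

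**What to change.** 1. In the Synopsis and Sections 3.1 and 7.1.1, keep the consent count and add the number and proportion of consented patients randomized within three months of enrollment, with an exact 95% confidence interval. Have the sponsor set a minimum in advance, and base the feasibility conclusion on both parts. State the minimum as a proportion so that it stays defined if consents differ from 40. The 75% in step 5 only shows how such a rule behaves; the value is the sponsor's choice.
2. State whether 40, and 20 per year, are consents or randomizations, and reconcile the Synopsis figure of 20 per arm with the consent definition in Section 3.1.
3. As a minor wording change, let Section 4 refer to patients enrolled (signed consent), in line with Sections 3.1 and 7.1.1.

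The cost is text changes and one sponsor decision. No new data are needed, since the rate reaching randomization is already to be reported under Section 7.1.2. Feasibility becomes harder to conclude, and the primary result closes up to three months after the last consent.

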### 3.2 Secondary Endpoint

- Successful randomization of patients
- Compliance with treatment and data collection as outlined in the protocol
- Evaluate enrollment rate and quality of data of patients who are not local
- Rate of IST resumption (discontinuation IST arm)/increase IST dose (continuation IST arm) by 12 months after randomization

- New chronic GVHD manifestations and/or worsening of existing manifestations, recurrent malignancy by 12 months after randomization, grade  $\geq 3$  infections, and grade  $\geq 3$  organ toxicity.

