## 7.2. Sample Size and Power

This feasibility study is to assess the ability to enroll and randomize patients with chronic GVHD to discontinuation versus continuation of IST. Sample size of 40 patients is based on the anticipated availability of eligible patients. Although the study is not powered based on a specific null hypothesis, if 20 patients are enrolled in each arm, we will have 83% power to see statistically significant difference between two arms (at the two-sided level of 0.1) if the true 12 months rate of IST resumption in discontinuation IST arm is 75% and true 12 months rate of increase IST dose in investigation arm is 30%.

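### The 12-month IST endpoint counts different events in the two arms and leaves the continuation arm at most 3 months off IST, so it cannot separate delayed from prevented flares

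*Combined protocol and SAP*

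**What the plan says.** All references are to the combined protocol and SAP.

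- **Endpoint.** Section 3.2 lists "Rate of IST resumption (discontinuation IST arm)/increase IST dose (continuation IST arm) by 12 months after randomization"; the synopsis has the same split. Section 7.2 carries it into the power statement: 75% resumption in the discontinuation arm, against an assumption that the "true 12 months rate of increase IST dose in investigation arm is 30"%.
- **Treatment and follow-up.** Under section 6.1, continuation patients "will continue a fixed dose IST for an additional 9 months with no taper. After 9 months, IST may be tapered". Active follow-up ends 12 months after randomization. Sections 6.4 and 6.5 then add annual chart review, which includes GVHD and IST status, but no endpoint uses it.
- **Retrospective data.** Section 1 reports that, of patients who stopped IST at least once, "46% of these patients required resumption of IST after a median of 3.4 months off therapy (IQR 2.1-8.0" months). It justifies the 9-month period by data showing "that >75% of patients who resumed IST after discontinuation, restarted within 9 months of IST discontinuation".
- **Purpose.** Section 2.2 includes the objective "Assess whether prolonged IST decreases the need for pulses of high dose IST". Section 6.2 gives the hypothesis that prolonged low-dose IST prevents exacerbation. Section 7.1.2 makes the secondary analyses descriptive and also proposes Fisher's exact test between arms.

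**The concern.** There are two separate problems.

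**The event.** A continuation patient who tapers after month 9, stops and restarts has resumed IST, but that arm's event is a dose increase. A discontinuation patient whose dose is raised, or who is given another agent, before reaching zero has not resumed anything. Neither is counted on a literal reading. The first omission lowers the continuation rate and the second lowers the discontinuation rate. The documents give no frequency for either, so the net direction is unknown. The monthly contact in section 6.5 asks only whether IST was restarted, which is the event of one arm.

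**The time at risk.** By month 12 the discontinuation arm may have been off IST for most of a year, and the continuation arm for a few weeks or not at all. A lower rate in the continuation arm could mean that flares were prevented or only that they have not yet happened.

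At stake is how the result is read. The hypothesis concerns prevention, and section 1 says "Information from this feasibility study are necessary to help us design a larger study and apply for external funding". A reader of the 12-month table should know that it does not test prevention.

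**Working it through.** **1. The plan's own figure.** Enumerating the two-sided Fisher test at 0.10 with 20 per arm and true rates of 75% and 30% gives 82.3% power, against the stated 83%. The figure reproduces. The issue is what the two rates count.

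**2. Time off IST.** With 9 months at fixed dose and a taper of T months, time off IST at month 12 is at most 12 - 9 - T = 3 - T months. It is shorter if randomization precedes reaching the continuation dose, as section 6.1 allows. The 9 months off IST that section 1 treats as the main risk period is complete only at 9 + T + 9 = 18 + T months. Month 24 covers it for tapers up to 24 - 18 = 6 months.

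**3. What can be seen by month 12 if nothing is prevented.** Assume that patients who stop after 9 extra months resume at the retrospective rate (46%) and with its timing (quartiles 2.1, 3.4 and 8.0 months).

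- Continuation arm: 3 < 3.4, so at most half of eventual resumptions can appear, 0.46 x 0.50 = 23% of patients. With a taper over 3 - 2.1 = 0.9 months, it is under a quarter, 0.46 x 0.25 = 11.5%.
- Discontinuation arm: if IST is off within 4 months of randomization, at least 12 - 4 = 8.0 months remain. At least three quarters then appear, 0.46 x 0.75 = 34.5%.

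**4. Delay-only gap on one common event.** Let F be a split log-normal curve through the three quartiles: F(t) = Phi(ln(t/3.4)/s), with s = 0.714 below 3.4 months and 1.269 above. This gives F(1) = 0.04, F(2) = 0.23, F(3) = 0.43, F(12) = 0.84, F(15) = 0.88 and F(24) = 0.94. Both arms have the same taper T and no taper flares. Let q be the share of continuation patients with a dose increase while on IST.

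- Discontinuation: 0.46 F(12 - T) at month 12; 0.46 F(24 - T) at month 24.
- Continuation: q + (1 - q) 0.46 F(3 - T) at month 12; q + (1 - q) 0.46 F(15 - T) at month 24.

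| T (months) | Month 12, q = 0 | Gap | Month 24, q = 0 | Gap | Month-12 gap, q = 20% |
|---|---|---|---|---|---|
| 0 | 38.6% vs 19.8% | 18.8 | 43.2% vs 40.4% | 2.7 | 2.8 |
| 1 | 37.8% vs 10.5% | 27.3 | 43.0% vs 39.9% | 3.1 | 9.4 |
| 2 | 36.9% vs 2.0% | 34.9 | 42.8% vs 39.3% | 3.4 | 15.3 |
| 3 | 35.8% vs 0% | 35.8 | 42.5% vs 38.6% | 3.9 | 15.8 |

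Gaps are in percentage points, discontinuation minus continuation. T and q are assumptions; the documents give neither.

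**5. Precision at month 24.** The 95% half-width for a difference is 1.96 x sqrt(2p(1 - p)/20), which is 0.30 at p = 0.40 and 0.31 at p = 0.50.

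**The case against.** **The gap is fragile.** This is the strongest objection, and it stands. With q = 20% the 12-month gap falls to 3-16 points. At q = 30%, which is the section 7.2 rate if it refers to increases while on IST, it is -5 to +6. The model also adds q on top of the 46%: at q = 20% the continuation arm's eventual rate is 0.20 + 0.80 x 0.46 = 57%, and the month-24 gap is -8 to -9 points. That is no longer pure delay, so the size of the artefact is not established. The 46% and its quartiles may not suit every patient either. Section 1 adds "Among patients stopping IST a second time, 30% restarted at a median of 6 months", and eligibility is not limited to first stops.

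**The data are largely captured.** This stands in part. Sections 6.1 and 6.4 schedule assessments at resumption or dose increase without regard to arm, and the survey form has an IST-change time point. The gap is in the endpoint definition and the monthly question. Section 3.2 also has a GVHD endpoint common to both arms, but active follow-up for it ends at month 12 too.

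**Stronger readings.** A reader might infer that the 12-month comparison is invalid. It is not: follow-up from randomization is equal, and with a common event it compares two strategies fairly. A reader might infer that the wording favours continuation, but the omissions oppose each other and their frequencies are unknown. A reader might also infer that the later trial would be mis-sized. Sections 1 and 6.2 say what this study must show: enrollment, randomization, adherence and whether the retrospective resumption findings hold. Nothing says that the between-arm difference will set the next sample size.

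**Conclusion.** The point holds in a limited form. Two facts rest on the text alone: the endpoint counts different events by arm, and an adherent continuation patient has at most 3 months off IST by month 12. It follows that a 12-month difference cannot separate postponed from prevented flares, even with a common event.

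The size is uncertain. The 23% ceiling and the gaps of 19-36 points at 12 months and 3-4 at 24 assume that the extra treatment prevents nothing and that the retrospective rate and timing apply. The gaps also assume no on-IST increases or taper flares. They illustrate the mechanism and do not estimate a bias in this trial.

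The analysis is secondary and descriptive, and the primary accrual endpoint and stopping rule are unaffected. Importance is minor to moderate, and the change is worth making because it is cheap.

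**What to change.** (a) In the synopsis and sections 3.2, 7.1.2 and 7.2, compare the arms on one common event: first GVHD-driven escalation of systemic IST after randomization, meaning a restart, a dose increase or an added systemic agent. Ask about it in the same words in both arms at the monthly contact in section 6.5. Keep discontinuation-arm resumption as a separate descriptive rate, because it is needed to check the retrospective data. Do not present the common event as a measure of the high-dose pulses in section 2.2, since it does not require a high dose.

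(b) From the annual chart review already planned in section 6.4, record the dates of escalation and of stopping IST. Report by arm the cumulative incidence of the same event at about 24 months from randomization, descriptively, with death and relapse as competing events. Section 6.5 continues chart review after relapse.

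(c) State in section 7.1.2 that the 12-month result compares strategies and cannot separate delay from prevention.

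The cost is some rewording, one changed question and modest extra chart abstraction, since section 6.4 lists IST status but not dated escalations. Chart data will be less certain for patients who are not local, and the later result comes 12 months after the main one. At about +/-30 points, (b) informs the question of delay or prevention but does not settle it. Treatment, visits, sample size, primary endpoint and stopping rule stay as they are.
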